4.3.2.5 PK Parameters

4.3.2.5.1 AUC_{0-t}

AUC_{0-t} is calculated using the same methods as described in section 4.3.2.1.

4.3.2.5.2 Baseline Adjusted AUC_{0-t}

Baseline adjusted AUC_{0-t} is calculated using the same methods as described in section 4.3.2.3.5

4.3.2.5.3 AUC_{0-60}

$AUC_{0-60\text{min}}$ is calculated using the same methods as described in section 4.3.2.1.

- If the “60 minute” insulin value actual collection time is before 55 minutes or after 65 minutes, then AUC_{0-60} will be set as missing.
- However, if the “60 minute” reading actual collection time is between 55 and 65 minutes, the AUC_{0-60} will be calculated using the available value.

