4.2.2 Per Protocol Time Points Vs Actual Time Points

Actual time points will be used for the all parameter calculation unless otherwise specified. Per protocol time may be used if the by each time point summary is needed.

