4.3.2.3.3 AUC_{0-t}

The AUC_{0-t} of GIR over wear time will be calculated using trapezoid rule and the actual time points. Missing data for the calculation of the AUC will be handled as followed:

1. If the reading for Time 0 is missing, it will be the average of up to 3 prior readings. However, if there is no prior readings available, it will be assumed to be 0
2. If the reading at (actual) time t ($t < 300$ min) is missing, it will be imputed with linear interpolation
3. If the reading at $t=300$ min is missing:
 - a. The reading at $t=300$ min will be imputed using the regression line obtained when estimate λ (section 4.3.2.3.1).
 - b. If λ is missing, AUC_{0-t} will be set as missing.

4.3.2.3.4 $AUC_{0-\infty}$

$AUC_{0-\infty}$ is estimated as

$$AUC_{0-\infty} = AUC_{0-last} + AUC_{last}, \text{ where } AUC_{last} = GIR_{last}/\lambda$$

If λ is missing, then $AUC_{0-\infty}$ is set as missing.

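### The AUC0-60 rule in the SAP sets recoverable values to missing and does not say that the area stops at 60 minutes

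*SAP*

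**What the plan says.** The protocol synopsis (Secondary Endpoints 2) names AUC0-60 as the early-exposure PK endpoint. SAP 4.4.4.2.2 tests the PK AUCs between devices at a two-sided 0.05 level.

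SAP 4.3.2.5.3 has three parts:

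- The method "is calculated using the same methods as described in section 4.3.2.1". Section 4.3.2.1 deals with curves that have several peaks or none and contains no integration rule.
- AUC0-60 is missing if the 60-minute "insulin value actual collection time is before 55 minutes or after 65 minutes".
- For a draw between 55 and 65 minutes, AUC0-60 "will be calculated using the available value".

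Two general rules bear on this. SAP 4.2.2 states: "Actual time points will be used for the all parameter calculation unless otherwise specified". SAP 4.3.2.3.3, where the AUC method is actually set out, says the area "will be calculated using trapezoid rule and the actual time points"; for a reading before 300 minutes that "is missing, it will be imputed with linear interpolation".

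Table 6 of the protocol schedules draws at 50, 55, 60, 70 and 80 minutes, all of the 1.5 mL size that protocol 6.1.1.5 assigns to glucose plus insulin.

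**The concern.** There are two separate problems.

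**Lost values.** A draw at 66 minutes makes AUC0-60 missing, although the samples at 55 and 66 minutes lie on either side of 60. If the general interpolation rule is meant to cover PK AUCs, a 60-minute sample that was never drawn would be filled in, while one drawn a minute outside the window removes the parameter. The synopsis also lists t = 60 among the AUC(0-t) endpoints, and the section for those (SAP 4.3.2.5.1) has no window. The same area could then be missing under one name and present under the other.

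**Unstated upper limit.** With actual times and the trapezoid rule, the last trapezoid ends where the last sample lies. One profile might cover 57 minutes and another 63, both labelled AUC0-60. Insulin concentration around 60 minutes can be well above zero, so a few minutes matter.

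The endpoint is close to the device's rationale: protocol 2.2.1 reports a larger surface-to-volume ratio for the multi-port cannula, and protocol 2.2.3 cites a dispersed-injection study with greater insulin area in the first 60 minutes. SAP 2.5 records that the study was terminated after the seventh subject completed. Seven completers with at most 2 × 4 = 8 clamps each supply at most 56 values, so avoidable losses and noise are unwelcome.

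**Working it through.** The plan gives no figure for this endpoint, so there is none to reproduce. The check sizes the effect of the draw time under each reading of the rule.

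**Inputs.** Sampling times come from Table 6 (0, 3, 6, 9, 12, 15, then every 5 minutes to 60, then 70, 80, 90). The window of 55 to 65 minutes comes from SAP 4.3.2.5.3. The curve shapes are assumptions, since the documents give no insulin profile.

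**Approximation.** If the draw is δ minutes off and the area ends at the draw, the relative change is about (δ/60) × C(60) / (mean C over 0-60).

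**Simple shapes, area ending at draw time T, relative to 60:**

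- Flat: T/60. 55/60 = 0.917; 65/60 = 1.083.
- Linear rise to 30 minutes, then plateau: (15 + T − 30)/45. 40/45 = 0.889; 50/45 = 1.111.
- Linear rise throughout: (T/60)². (55/60)² = 0.840; (65/60)² = 1.174.

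**Absorption curves.** C(t) ∝ exp(−ke·t) − exp(−ka·t), with ka = 1.5·ke and ke chosen so that tmax = ln(1.5)/(0.5·ke). For example, tmax = 60 gives ke = 0.4055/30 = 0.0135 per minute. Area to the actual draw time, as a percentage of the true AUC0-60 (the 55-minute column was run at 55.01):

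| Assumed tmax (min) | Draw at 55 | Draw at 58 | Draw at 62 | Draw at 65 |
|---|---|---|---|---|
| 30 | 91.8 | 96.6 | 102.7 | 107.1 |
| 45 | 89.6 | 95.7 | 103.8 | 109.8 |
| 60 | 88.3 | 95.2 | 104.5 | 111.4 |
| 75 | 87.5 | 94.9 | 104.9 | 112.4 |
| 90 | 87.0 | 94.7 | 105.2 | 113.2 |

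A draw at the window edge therefore shifts the value by about 7-13%, and a 2-minute deviation by about 3-5%. The flat case is a reference, not a strict lower limit: a curve already falling by 60 minutes can give slightly less (7.1% at 65 minutes for tmax 30).

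**Alternative reading.** If the reading is placed at 60 minutes whatever its draw time, the result is 99.4-100.0% of the true value across the same curves and draw times, an error of at most 0.6%.

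**Interpolating to exactly 60.** Using the nearest actual-time samples on each side, the result is 99.7-99.9% of the true value at every draw time tried from 54 to 66 minutes. That includes 54 and 66, which the SAP sets to missing. The remaining 0.1-0.3% is mainly ordinary trapezoid error, present even with a draw at exactly 60.

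**The case against.** The strongest reply is that the SAP never says the area ends at the draw time. A tolerance window often means that a reading inside it stands for the nominal time, and the actual-time rule allows exceptions. On that reading the error is negligible. This stands in part: the larger figures depend on a reading that the text supports but does not state. It does not remove the point, because the cross-referenced section does not settle the limit and the loss outside the window is explicit on either reading.

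Second, these are supervised clamps with a draw scheduled every 5 minutes up to 60, so a 60-minute draw at 55 would coincide with the previous one. Window-edge errors are probably uncommon. That stands: the documents report no actual deviations.

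Third, a pre-specified window with missing outside it is transparent, and the general interpolation rule may keep the 60-minute area available under AUC(0-t). Transparency is granted. But two rules giving different answers for one quantity is a reason to reconcile them.

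A reader might infer more than the documents support:

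- That AUC0-60 is wrong by 8-17% in this trial. Those figures need window-edge draws, one reading of the rule and a flat or steadily rising profile.
- That the device comparison is biased. Nothing suggests that draw times differ by device; unrelated deviations add noise.
- That only seven participants are analysed. Seven is the number of completers. The ITT population, primary for PK, admits any eligible randomised participant with at least one clamp, so it could be larger.

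**Conclusion.** The point holds as a minor one about how a tested secondary endpoint is derived. It is certain from the text that AUC0-60 goes missing outside 55-65 minutes when scheduled samples on either side would allow its calculation, and that no step brings the curve to 60 minutes. That the area ends at the draw time is the natural reading of 4.2.2, 4.3.2.3.3 and 4.3.2.5.3 together, but it remains an inference.

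The size depends on that inference, on assumed curves and on draw times that are not reported. If the area ends at 60 by convention, only the avoidable missing values remain. The number of values lost cannot be estimated from the documents. The primary analysis, the slope of ln AUC0-300 of GIR, does not use this rule and is unaffected.

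**What to change.** Replace the window rule in SAP 4.3.2.5.3 with this:

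- Compute AUC0-60 by the trapezoid rule on actual times, from 0 to exactly 60 minutes.
- Obtain the 60-minute concentration by linear interpolation between the nearest actual-time samples on each side, unless a sample was drawn at exactly 60.
- Set AUC0-60 to missing only if no samples bracket 60 minutes within a maximum gap fixed before analysis. The scheduled neighbours are 15 minutes apart (55 and 70), or 20 if the 55-minute sample has no insulin result, so the limit should allow at least that plus some drift.

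The same rule may serve the other PK AUC0-t with t below 300, which would make AUC0-60 and AUC(0-t) at t = 60 agree. It should not be extended to AUC0-300. No sample is scheduled after 300 minutes, so a bracketing requirement would make AUC0-300 missing whenever the last draw came early. The t = 300 imputation in 4.3.2.3.3 should stay.

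Correct the method references in 4.3.2.5.1 and 4.3.2.5.3 from 4.3.2.1 to 4.3.2.3.3.

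The cost is a short SAP paragraph, two corrected references and a few lines of code. No new data are needed. A listing of actual 60-minute draw times by device and day would show whether the change matters in practice.

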4.3.2.5.4 Percentage of AUC_{0-300} and Coefficient of Variability (CV) AUC

These parameters will be calculated with the same methods as described in section 4.3.2.4.5

4.3.2.5.5 Mean-Residence Time (MRT) of Insulin

MRT of insulin will be calculated with the same methods as described in section 0.

4.3.2.5.6 Maximum Insulin Concentration (C_{max})

C_{max} will be calculated with the same methods as described in section 4.3.2.3.1

4.3.2.5.7 Time-to-Maximum Insulin Concentration (T_{max})

T_{max} will be calculated with the same methods as described in section 4.3.2.4.1.

- If C_{max} is missing, $t_{max(GIR)}$ will also be set as missing.

4.3.2.5.8 Time-to-50% Maximum Insulin Concentration [$t_{50,early}$ & $t_{50,late}$]

$t_{50,early}$ & $t_{50,late}$ will be calculated with the same methods as described in section 4.3.2.4.2.

4.3.2.6 Continues Glucose Monitor (CGM) Blood Glucose (BG)

Blood glucose concentration is captured in a commercial CGM device and the data is exported into a csv or excel file and imported into SAS.

- CGM is coming from two sources: Dexcom CGM and Medtronic CGM using by some automatic Pump.
- The data from Dexcom CGM will be used for analyses, only if there are missing data in Dexcom CGM, the data from Medtronic Pump CGM will be used for substitution.

The mean daily CGM glucose, standard deviation (SD) of daily CGM glucose and time (%) spent in glucose range of daily CGM glucose will be summarized.

All CGM parameters will be based on out-patient days' data only.

4.3.2.6.1 Evaluable CGM Days

The CGM glucose is recorded every 5 minutes. Thus, for each day (24 hours, 0:00-23:59), there should be 288 data points recorded. However, in some cases, there might be fewer data points reported. In such case, using a 24-hour CGM interval with less than 288 data points will result in bias, as blood glucose concentrations may vary throughout the day.

For this reason, we will use the following process to select the evaluable CGM day (24-hour interval):

1. For each subject, we will use cubic spline to interpolate any missing intervals that are less than or equal to 2 hours (or 24 data points).
2. Then an evaluable CGM day will be the interval with at least 276 data points (or at least 23 hours).
3. We will only use these evaluable CGM day in the following analyses. The choice of the number 276 is arbitrary and based on past experience of CGM analyses.

In some rare cases, we may have duplicated glucose readings of the CGM. Duplication is defined as two or more records with the exact same subject ID, date and time (including sections).

- Duplications will be averaged and the mean glucose concentration will be used as the reading for this date and time of the subject.

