4.3.2.6.4 Time (%) Spent in Glucose Range

The time (%) spent in glucose range is estimated as:

$$\text{Time}(\%) \text{ in } BG < 54 \text{ mg/dL} = \frac{\# \text{ of CGM BG readings } < 54 \text{ mg/dL}}{\# \text{ of all available CGM BG readings}}$$

$$\text{Time}(\%) \text{ in } BG < 70 \text{ mg/dL} = \frac{\# \text{ of CGM BG readings } < 70 \text{ mg/dL}}{\# \text{ of all available CGM BG readings}}$$

$$\text{Time}(\%) \text{ in } BG \geq 70 \text{ and } \leq 140 \text{ mg/dL} = \frac{\# \text{ of CGM BG readings } \geq 70 \text{ and } \leq 140 \text{ mg/dL}}{\# \text{ of all available CGM BG readings}}$$

$$\text{Time}(\%) \text{ in } BG \geq 70 \text{ and } \leq 180 \text{ mg/dL} = \frac{\# \text{ of CGM BG readings } \geq 70 \text{ and } \leq 180 \text{ mg/dL}}{\# \text{ of all available CGM BG readings}}$$

$$\text{Time}(\%) \text{ in } BG > 140 \text{ mg/dL} = \frac{\# \text{ of CGM BG readings } > 140 \text{ mg/dL}}{\# \text{ of all available CGM BG readings}}$$

$$\text{Time}(\%) \text{ in } BG > 180 \text{ mg/dL} = \frac{\# \text{ of CGM BG readings } > 180 \text{ mg/dL}}{\# \text{ of all available CGM BG readings}}$$

$$\text{Time}(\%) \text{ in } BG > 240 \text{ mg/dL} = \frac{\# \text{ of CGM BG readings } > 240 \text{ mg/dL}}{\# \text{ of all available CGM BG readings}}$$

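### The evaluable-CGM-day test counts points after gap filling, with no daily limit on filled time, so it can keep a day that is 75% measured and exclude one that is 91% measured

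*SAP*

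**What the plan says.** SAP 4.3.2.6.1 starts from the sampling rate: "The CGM glucose is recorded every 5 minutes", so for a calendar day "there should be 288 data points recorded". It notes that days with fewer points can bias the summaries, and gives a numbered procedure to deal with this.

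- Step 1: for each participant, "we will use cubic spline to interpolate any missing intervals that are less than or equal to 2 hours (or 24 data points".
- Step 2: "Then an evaluable CGM day will be the interval with at least 276 data points (or at least 23 hours".
- Step 3: "We will only use these evaluable CGM day in the following analyses". The SAP adds: "The choice of the number 276 is arbitrary and based on past experience of CGM analyses".

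SAP 4.3.2.6 names a second source: "only if there are missing data in Dexcom CGM, the data from Medtronic Pump CGM will be used for substitution". It does not say whether this substitution comes before or after the spline. The same section restricts CGM parameters to out-patient days.

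The time-in-range formulas in SAP 4.3.2.6.4 divide by the number "of all available CGM BG readings". The mean and SD in 4.3.2.6.2 and 4.3.2.6.3 likewise use all available values, and the CV in 4.3.2.6.5 is their ratio. None of these sections says whether a filled value is an available reading.

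**The concern.** The rule exists to keep incomplete days from biasing the CGM summaries. For that, its threshold has to respond to how much of the day was measured. Because the count is taken after filling, it responds almost only to whether one gap exceeded the fill limit. A day assembled from many shorter gaps always looks complete.

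The days kept feed all the CGM metrics in the Protocol synopsis under Secondary Endpoints 3, including time below 54 mg/dL. The SAP (2.5) records that the study was stopped after the seventh participant completed, so there are few days to average over. Clamps fall on days 0, 3, 5 and 7, and participants arrive the evening before each clamp (Protocol 6.1.1.4). The SAP does not define an out-patient day. On my reading there are between one (day 1, wholly away from the clinic) and four (days 1, 2, 4 and 6, clamp-free) per wear period. With so few, the selection of single days can show in a summary.

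**Working it through.** **Inputs (all SAP 4.3.2.6.1).** Readings every 5 minutes; 288 expected per day; gaps of up to 24 points filled; threshold of 276 points.

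**The plan's own equivalences.** 288 × 5 / 60 = 24 h; 276 × 5 / 60 = 23 h; 24 × 5 / 60 = 2 h. All agree with the SAP.

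**The rule as a formula.** Let a day have gaps of g₁, g₂, … missing points, all lying inside the day.

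- Measured: M = 288 − Σg
- Filled: F = sum of those g that are 24 or less
- Counted: N = M + F; the day is kept if N ≥ 276

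| Day | Measured M | Filled F | Counted N | Result |
|---|---|---|---|---|
| One 24-point gap | 264 (91.7%) | 24 (2 h) | 288 | kept |
| One 25-point gap | 263 (91.3%) | 0 | 263 | excluded |
| Three 24-point gaps | 216 (75.0%) | 72 (6 h) | 288 | kept |
| Eleven 24-point gaps (limiting case) | 24 (8.3%) | 264 (22 h) | 288 | kept |

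The excluded 25-point day has 263 − 216 = 47 more measured readings than the three-gap day that is kept.

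**Does 276 decide anything?** A single gap inside the day leaves N = 288 if g ≤ 24 and N ≤ 263 if g ≥ 25. Values from 264 to 287 cannot occur, so any threshold from 264 to 288 would classify such a day identically. The same holds for several gaps inside the day, since each is either filled or removes at least 25 points. The cut-off can matter in two situations:

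- A gap at the start or end of a record has no reading on one side to interpolate from. Losing 12 points leaves 276 (kept); losing 13 leaves 275 (excluded).
- An unfilled gap can cross midnight. For example, 30 points split 10 and 20 leave 278 (kept) and 268 (excluded).

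**Could 276 mean measured readings?** Then a day with one permitted 24-point gap (264) would fail, as would a day with one 65-minute gap (288 − 13 = 275). Filling any gap of 13 to 24 points inside a day would then serve no purpose for that day. Step 2 also follows step 1 explicitly. The count after filling is the reading that fits the text.

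**What could enter the summaries.** If filled values count as readings, 72 / 288 = 25% of the denominator on the three-gap day is interpolated.

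**Can a spline leave the range of its flanking readings?** Yes. The following uses slopes and levels that I have assumed. With 24 points missing, the flanking readings are 25 × 5 = 125 minutes apart. A cubic matched to the slopes at both edges is displaced at its midpoint by 125 × (difference in edge slopes) / 8. For glucose falling into and rising out of the gap at the same rate:

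- 0.5 mg/dL/min: 125 × 1 / 8 = 15.6 mg/dL below the flanks
- 1.0 mg/dL/min: 125 × 2 / 8 = 31.3 mg/dL
- 1.5 mg/dL/min: 125 × 3 / 8 = 46.9 mg/dL

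From flanks of 100 mg/dL, the middle case reaches about 69, under the 70 mg/dL limit. From flanks of 120 it reaches about 89 and crosses no low-glucose limit. This shows that it can happen, not how often.

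**The case against.** The strongest case on the other side has four parts.

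**The spline.** A reader might infer that the spline manufactures hypoglycemia and should be replaced by linear interpolation. The documents do not support that. If glucose falls into a gap and rises out of it, it must have dipped in between; the spline draws such a dip, and a straight line would hide it. Which method is closer depends on glucose shape, sensor noise and gap frequency, and the documents give none of these. Any simulated rate of false lows would reflect whatever was assumed. This part stands: spline versus linear is a trade-off.

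**Use of the filled values.** A reader might take it as settled that filled values enter the endpoints as if measured. The formulas do not say so. That they are used is suggested by their counting toward evaluability, but it remains an inference.

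**Reach of the rule.** It would be too strong to say that a day can fail only through one gap longer than 2 hours. Gaps at the ends of a record and gaps across midnight are exceptions, as shown above.

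**Likelihood.** Pump CGM data may close some gaps, site staff review CGM data at clinic visits, and entry requires about 80% capture in screening (Protocol 5.2 and 6.1.1.2). Nothing suggests that days with three 2-hour gaps will be common. That is fair, but the second source exists only for some pumps, its order relative to the spline is not stated, and screening capture does not bound missing data in the wear periods.

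None of this alters the reversed ranking of days, which follows from the SAP text and needs no assumption about glucose.

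**Conclusion.** The evaluable-day test does not measure completeness. As written it can keep a day with 216 measured readings (75%) and exclude one with 263 (91%), and for a single gap within the day the 276 cut-off never decides the outcome. This rests on counting missing points, as the SAP's own 24-point limit does, and on taking steps 1 and 2 in their stated order.

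That several hours of interpolated values per day could reach the time-in-range, SD and CV summaries is conditional on filled values counting as readings. No frequency or size of distortion can be given from the documents.

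The consequence is small. Under SAP 4.4.4.2.4 the CGM endpoints are summarized descriptively, and the clamp-based slope analysis of glucose infusion is untouched. This is a cheap improvement, worth making because the present rule works against its stated purpose.

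**What to change.** Replace step 2 of SAP 4.3.2.6.1 by a test on measured data: *a calendar day is evaluable only if at least 264 of its 288 five-minute readings were measured, counted after any substitution of Medtronic for missing Dexcom readings and before interpolation.* Since 288 − 264 = 24 points, total filled time is then at most the 2 hours already accepted for one gap. Apply the rule to all CGM metrics. The three-gap day (216) drops out and the day with one 2-hour gap (264) stays.

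Also state that substitution precedes interpolation, and say whether filled values count in the mean, SD, CV and time-in-range formulas. The spline can remain. At most, add a sensitivity summary of the low-glucose metrics from measured readings only.

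The cost is SAP wording and a few lines of code. Days with several gaps totaling more than 2 hours are lost, and the 263-reading day remains excluded, though no poorer day is then kept ahead of it. Days missing 13 to 24 points at the edge of a record (264 to 275 measured) would be newly admitted unless the 276-point test is retained as a second condition. The sponsor should choose and say which.

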4.3.2.6.2 Mean Daily CGM Glucose

The mean daily CGM glucose is calculated as:

$$\text{Mean Daily CGM BG} = \frac{\text{Sum of (all available CGM BG)}}{\text{\# of all available CGM BG}}$$

4.3.2.6.3 SD of Daily CGM Glucose

Let $N = \#$ of all available CGM BG, $i = \text{index of each BG}$, then SD of Daily CGM Glucose is calculated as:

$$\text{SD of Daily CGM BG} = \sqrt{\frac{\sum_{i=1}^N (BG_i - \text{MeanBG})^2}{(N - 1)}}$$

4.3.2.6.4 Time (%) Spent in Glucose Range

The time (%) spent in glucose range is estimated as:

$$\text{Time}(\%) \text{ in } BG < 54 \text{ mg/dL} = \frac{\# \text{ of CGM BG readings } < 54 \text{ mg/dL}}{\# \text{ of all available CGM BG readings}}$$

$$\text{Time}(\%) \text{ in } BG < 70 \text{ mg/dL} = \frac{\# \text{ of CGM BG readings } < 70 \text{ mg/dL}}{\# \text{ of all available CGM BG readings}}$$

$$\text{Time}(\%) \text{ in } BG \geq 70 \text{ and } \leq 140 \text{ mg/dL} = \frac{\# \text{ of CGM BG readings } \geq 70 \text{ and } \leq 140 \text{ mg/dL}}{\# \text{ of all available CGM BG readings}}$$

$$\text{Time}(\%) \text{ in } BG \geq 70 \text{ and } \leq 180 \text{ mg/dL} = \frac{\# \text{ of CGM BG readings } \geq 70 \text{ and } \leq 180 \text{ mg/dL}}{\# \text{ of all available CGM BG readings}}$$

$$\text{Time}(\%) \text{ in } BG > 140 \text{ mg/dL} = \frac{\# \text{ of CGM BG readings } > 140 \text{ mg/dL}}{\# \text{ of all available CGM BG readings}}$$

$$\text{Time}(\%) \text{ in } BG > 180 \text{ mg/dL} = \frac{\# \text{ of CGM BG readings } > 180 \text{ mg/dL}}{\# \text{ of all available CGM BG readings}}$$

$$\text{Time}(\%) \text{ in } BG > 240 \text{ mg/dL} = \frac{\# \text{ of CGM BG readings } > 240 \text{ mg/dL}}{\# \text{ of all available CGM BG readings}}$$

